2.8.2 Deaths

Separate summaries and listings will be provided for deaths for each treatment period. The number of deaths resulting from SAEs suspected to be related to study treatment and SAEs irrespective of study treatment relationship will be provided by SOC and PT.

2.8.3 Laboratory data

The summary of laboratory evaluations will be presented for three groups of laboratory tests (hematology, chemistry and urinalysis).

For urinalysis, only data listing will be presented.

Descriptive summary statistics for the change from baseline to each study visit will be presented. These descriptive summaries will be presented by laboratory test and treatment group. Change from baseline will only be summarized for patients with both baseline and post baseline values and will be calculated as:

$$\text{change from baseline} = \text{post baseline value} - \text{baseline value}$$

For each parameter, the maximum change from baseline within each study period will be analyzed analogously.

Table 2.8-1 Liver-related events

Parameter	Criterion
ALT	>3xULN; >5xULN; >8xULN; >10xULN, >20xULN
AST	>3xULN; >5xULN; >8xULN >10xULN; >20xULN
ALT or AST	>3xULN; >5xULN; >8xULN >10xULN; >20xULN
TBL	>1.5xULN, >2xULN, >3xULN,
ALP	>2xULN, >3xULN. >5xULN
ALT or AST & TBL	ALT or AST >3xULN & TBL >2xULN; ALT or AST >5xULN & TBL >2xULN; ALT or AST >8xULN & TBL >2xULN; ALT or AST >10xULN & TBL >2xULN
ALP & TBL	ALP >3xULN & TBL >2xULN ALP >5xULN & TBL >2xULN
ALT or AST & TBL & ALP	ALT or AST >3xULN & TBL >2xULN & ALP <2xULN (Hy's Law) Note: elevated ALP may suggest obstruction as a consequence of gall bladder or bile duct disease; ALP may also be increased in malignancy. FDA therefore terms Hy's Law cases as indicators of pure hepatocellular injury. This does not mean that cases of ALT or AST >3xULN & TBL >2xULN & ALP \geq 2xULN may not result in severe DILI.

Notes:

In studies which enroll patients with pre-existing liver disease, baseline LFT may be increased above

ULN; in such a case it is meaningful to add the condition “and worse than baseline” to the abnormality Criteria

For a combined criterion to be fulfilled, all conditions have to be fulfilled on the same visit. The criteria are not mutually exclusive, e.g. a subject with ALT = 6.42xULN is counted for ALT >3xULN and ALT>5x ULN.

Individual subject data listings will be provided for patients with abnormal laboratory data. Data of patients with newly occurring or worsening liver enzyme abnormalities will be listed in an additional listing.

Separate summaries and listings will be provided for urine pregnancy results by visit for each treatment period.

Listing will be provided for all renal events captured in the study.

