#### **6.5.4.3 Urinalysis**

Dipsticks will be provided by the central laboratory to the sites for local urinalysis assessments. The measurements for standard parameters such as protein, glucose, blood and WBCs will be performed and results recorded in the appropriate eCRF page.

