## 7.4 Renal safety monitoring

The following 2 categories of abnormal renal laboratory values have to be considered during the course of the study:

- Serum event:
  - confirmed (after  $\geq 24$ h) increase in serum creatinine of  $\geq 25\%$  compared to Baseline during normal hydration status
- Urine event
  - new onset ( $\geq 1+$ ) proteinuria; confirmed by doubling in the urinary albumin-creatinine ratio or urinary protein-creatinine ratio (PCR) (if applicable)
  - new onset ( $\geq 1+$ ), hematuria or glycosuria

Every renal laboratory trigger or renal event should be followed up by the investigator or designated personnel at the trial site as summarized in [Appendix 3](#).

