#### **9.5.2.2 Laboratory data**

Laboratory evaluations will be summarized for 3 groups of laboratory tests (hematology, serum chemistry and urinalysis). Descriptive summary statistics for the change from Baseline in laboratory data at each study visit will be presented. These descriptive summaries will be presented by test group, laboratory test and treatment group. Change from Baseline will only be summarized for patients with both Baseline and post-Baseline assessments. For each parameter, the maximum change from Baseline within each study period will also be analyzed.

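### SAP 2.8.3 cuts the protocol's by-group urinalysis summary to a listing without declaring the change, so dipstick findings not reported as adverse events have no planned count by arm

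*SAP*

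**What the plan says.** Protocol 9.5.2.2 covers all three laboratory groups: "Laboratory evaluations will be summarized for 3 groups of laboratory tests (hematology, serum chemistry and urinalysis". It adds "These descriptive summaries will be presented by test group, laboratory test and treatment group", and makes no exception for urinalysis.

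SAP 2.8.3 begins in the same way: "The summary of laboratory evaluations will be presented for three groups of laboratory tests", with urinalysis named as the third group. It then says "For urinalysis, only data listing will be presented". For renal events the same section has a single line: "Listing will be provided for all renal events captured in the study".

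SAP Section 1 says that departures from the protocol are documented. SAP Section 4, the place for them, says there are none.

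Protocol 6.5.4.3 has the dipstick read at the site for protein, glucose, blood and white cells, with "results recorded in the appropriate eCRF page". Table 6-1 schedules it at Screening, Baseline and Weeks 4, 8, 12 and 24. Protocol 7.4 and Appendix 3 define urine events that start from a new dipstick finding of 1+ or more for protein, blood or glucose.

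**The concern.** A listing is not a summary by treatment group. It gives patient-level rows with no denominators, and reading rows as a comparison is unsafe when one group is three times the size of the other. With no real difference it suggests an excess on secukinumab, and a similar number of rows in each group would hide a higher rate on placebo.

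The SAP also leaves the programmer with two instructions for urinalysis, and a reader who relies on Section 4 would not know that a protocol output had been dropped. At stake is a pre-specified piece of comparative safety reporting. No data monitoring committee or interim analysis is planned, so the final report is the planned occasion for that comparison.

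**Working it through.** **Step 1. The texts side by side.**

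| Item | Protocol | SAP |
|---|---|---|
| Urinalysis | Summary by treatment group (9.5.2.2) | Summary, then listing only (2.8.3) |
| Renal events | Site follow-up criteria (7.4, Appendix 3); no analysis specified | Listing only (2.8.3) |
| Serum creatinine | In the chemistry panel (6.5.4.2), summarised (9.5.2.2) | Change from baseline and maximum change by group (2.8.3) |
| Declared changes | – | None (Section 4) |

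**Step 2. What other outputs pick up.** Under Protocol 7.1 an abnormal laboratory result is an adverse event only if it causes signs or symptoms, is judged clinically significant, or needs therapy. Results that qualify enter the by-treatment tables of SAP 2.8.1. An asymptomatic new 1+ dipstick result judged not clinically significant does not. No other output in SAP 2.8 counts it: Table 2.8-1 is restricted to liver criteria, the vital-sign counts in 2.8.4.2 do not apply, and the only urine result summarised is the pregnancy test.

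**Step 3. Denominators for Period 1.** The plan's figure is 332 (249 + 83), raised to 352 (264 + 88). It reproduces with the two-proportion formula at 3:1, two-sided 5%, 90% power, with continuity correction:

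- Weighted mean rate = (0.235 + 3 × 0.436)/4 = 0.38575; difference = 0.436 − 0.235 = 0.201.
- Uncorrected placebo n = [1.960 × √(4/3 × 0.38575 × 0.61425) + 1.2816 × √(0.235 × 0.765 + 0.436 × 0.564/3)]² / 0.201² = (1.1017 + 0.6557)²/0.0404 = 76.4.
- Corrected n = (76.4/4) × [1 + √(1 + 8/(3 × 76.4 × 0.201))]² = 82.9, so 83 on placebo and 4 × 83 = 332 in total.

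The arm sizes are not in dispute.

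**Step 4. What a listing would show with no drug effect.** Expected patients = risk × arm size. The documents give no event rate, so the risks are assumptions, equal in both groups.

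| Assumed risk | Secukinumab (264) | Placebo (88) |
|---|---|---|
| 2% | 5.3 | 1.8 |
| 5% | 13.2 | 4.4 |
| 10% | 26.4 | 8.8 |

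Conversely, 12 patients listed in each group would be 12/264 = 4.5% against 12/88 = 13.6%.

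**Step 5. Period 2.** There are five arms, all active. At the planned 43.6% response, and ignoring drop-out, A1 would have about 0.436 × 264 = 115 patients, A2 and A3 together about 264 − 115 = 149, and B1 and B2 together 88. Denominators per arm are needed here too.

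**Step 6. How much a table could show.** With equal risk p, the approximate 95% half-width for the Period 1 difference is 1.96 × √[p(1 − p)(1/264 + 1/88)]: 3.4 percentage points at 2%, 5.3 at 5% and 7.2 at 10%.

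**The case against.** The strongest reply has five parts.

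- **Adverse events are counted.** A reader might infer that the protocol's urine safety events are never counted by arm. The documents do not support that. Abnormalities that meet the adverse event criteria are tabulated by treatment, with separate tables for events leading to discontinuation, interruption or additional therapy. This stands, and it confines the gap to findings not reported as adverse events.
- **Serum renal function is summarised.** A reader might infer that a renal signal would go unseen. Creatinine change and maximum change are reported by group, and neither the protocol's listed risks (3.7) nor the SAP's events of special interest (2.8.1.1) include a renal topic. This stands.
- **The protocol promised no incidence table of renal events.** It asks for a urinalysis summary, and Section 7.4 and Appendix 3 guide follow-up at the site. This stands, so event tables cannot be claimed as a protocol requirement. The events also carry qualifiers: proteinuria is "confirmed by doubling in the urinary albumin-creatinine ratio or urinary protein-creatinine ratio (PCR) (if applicable", Appendix 3 excludes glycosuria due to diabetes and hematuria due to trauma, and among urine events it mentions interruption only in the proteinuria and ratio row. A dipstick count is therefore not a count of confirmed renal events.
- **The listing-only sentence is an exception to a general opening, and Protocol Section 9 defers details to the SAP.** This is a fair reading of the two SAP sentences. It does not meet the main point, because dropping a specified summary is a change to the analysis and Section 4 says there is none.
- **A listing can be tallied by hand and a table would be imprecise.** Both are true. The data are not lost, and a half-width of 5.3 points on a 5% base cannot exclude a doubling of risk. But a table at least gives the right denominators, without an unplanned tally after unblinding.

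**Conclusion.** The point holds as an undeclared departure from the protocol. SAP 2.8.3 replaces a by-group urinalysis summary with a listing, its opening sentence still promises the summary, and Section 4 declares nothing. The practical consequence is limited: dipstick abnormalities not reported as adverse events have no planned count by arm in either period.

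The illustration of about 5 versus 2 up to 26 versus 9 patients rests on assumed equal risks of 2% to 10% and on the planned 264 and 88. The Safety Set counts treated patients, so the actual denominators may differ slightly. The mismatch between the documents depends on none of these assumptions.

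The matter is minor and confined to safety reporting. The primary analysis, alpha and power are unaffected.

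**What to change.** In SAP 2.8.3, replace the listing-only sentence with a table, by arm and treatment period, of the number and percentage of patients with new-onset dipstick protein, blood or glucose of 1+ or more. A shift table from baseline would serve equally well for ordinal results. Use SAF-TP1 and SAF-TP2 as denominators, and state which baseline defines new onset in Period 2 (SAP 2.1.1 already takes Week 8 as the baseline for that period). Label the table as dipstick findings, not confirmed renal events, since albumin- and protein-creatinine ratios are not among the scheduled tests in Protocol 6.5.4. Keep both listings.

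If listing only is retained, declare it in SAP Section 4 with a reason, and remove urinalysis from the opening sentence of 2.8.3.

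An optional addition, not promised by the protocol, is a count of patients meeting the serum creatinine criteria: a rise of 25% or more (Section 7.4), or the bands of 25–49% and 50% or more (Appendix 3).

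The cost is one or two descriptive tables from dipstick results that are already scheduled and recorded on the eCRF. There is no new data collection and no change to sample size.

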2.8.4 Other safety data

2.8.4.1 ECG and cardiac imaging data

Not applicable.

2.8.4.2 Vital signs

Analysis in vital signs measurement using descriptive summary statistics for the change from baseline for each post-baseline visit will be performed. These descriptive summaries will be presented by vital sign and treatment group. Change from baseline will only be summarized for patients with both baseline and post-baseline values and will be calculated as:

$$\text{change from baseline} = \text{post-baseline value} - \text{baseline value}$$

The number and percentage of patients with newly occurring notable vital signs will be presented. Criteria for notable vital sign abnormalities are provided in Table 2.8-2 below.

Table 2.8-2 Criteria for notable vital sign abnormalities

Vital sign (unit)	Notable abnormalities (for hypertension)
Systolic blood pressure (mmHg)	$\geq 140 \text{ mmHg}$ or $< 90 \text{ mmHg}$
Diastolic blood pressure (mmHg)	$\geq 90 \text{ mmHg}$ or $< 60 \text{ mmHg}$
Pulse (bpm)	$> 100 \text{ bpm}$ or $< 60 \text{ bpm}$

2.9 Pharmacokinetic endpoints

Not applicable.

2.10 PD and PK/PD analyses

Not applicable.

2.11 Patient-reported outcomes

Variables related to health-related quality of life (HR-QoL) are described below. All HR-QoL variables will be evaluated based on the FAS-TP1 and FAS-TP2 population at (Baseline to Week 8) and (Week 8 to Week 24) respectively.

FACIT-Fatigue[®] score

- Change from baseline in FACIT-Fatigue[®] score for each treatment group at Week 8.
- Change from baseline in FACIT-Fatigue[®] score for each treatment group at Week 24.
- Change from Week 8 in FACIT-Fatigue[®] score for each treatment group at Week 24.

All FACIT scales are scored so that a high score is good.

To achieve this, we reverse response scores on negatively-phrased questions. The total score is then calculated as the sum of the un-weighted subscale scores.

Calculate the score only if at least 11 questions are answered.

Calculate the total score as mentioned in below table:

Item Number	Reverse Item?		Item Response	Item Score
1	4	-		=
2	4	-		=
3	4	-		=
4	4	-		=
5	4	-		=
6	4	-		=
7	0	+		=
8	0	+		=
9	4	-		=
10	4	-		=
11	4	-		=
12	4	-		=
13	4	-		=

Sum individual item scores: _____

Multiply by 13: _____

Divide by number of items answered: _____

Patient Accepted Symptoms State

- Proportion of patients in each treatment group with satisfactory PASS at Week 1, 2, 3, 4 and 8.
- Proportion of patients in each treatment group with satisfactory PASS at Week 12, 20 and 24.

ASAS Health Index

- Proportion of patients in each treatment group of achieving a minimal improvement (MCII) in ASAS health index at Week 8.
- Proportion of patients in each treatment group of achieving a minimal improvement (MCII) in ASAS health index at Week 24.

- Proportion of patients in each treatment group of achieving a significant improvement (SCI) in ASAS health index at Week 8.
- Proportion of patients in each treatment group of achieving a significant improvement (SCI) in ASAS health index at Week 24.
- Change from baseline in ASAS health index for each treatment group at Week 8 and Week 24.

Total Score calculation:

Total Score will be analyzed, if no more than 20% of data is missing. The total score is calculated as follows for respondents with one to a maximum of three missing responses

$$\text{Sumscore} = \{x/(N-m)\} * N$$

Where

x= Item summation score

N=Total no of items applicable (Items “I have lost interest in sex.” and “I have difficulty operating the pedals in my car” can be not applicable for few patients).

m=Number of missing Items

The definition of improvement is as follows:

- MCII (minimal clinically important improvement) \geq 1 point of decrease from previous ASAS HI measurement
- SCI (Significant clinically improvement) \geq 4 points of decrease from previous ASAS HI measurement

2.12 Biomarkers

Not applicable.

2.13 Other Exploratory analyses

All the exploratory efficacy evaluation will be performed on FAS-TP1 and FAS-TP2 population based on the corresponding treatment periods. Refer to [Table 1.2-1](#) of Section 1 for the list of exploratory endpoints.

The following exploratory efficacy variables will be analyzed on the FAS-TP1 and FAS-TP2 population at (Baseline to Week 8) and (Week 8 to Week 24) respectively for all applicable analysis visits unless otherwise specified.

- Spinal pain score: Average NRS spinal pain score will be calculated only if total and nocturnal pain score are non-missing.
- BASDAI score: It will be calculated based on the average of the non-missing answers available.
- ASDAS CRP
- Patient reported outcomes: FACIT-Fatigue[©], PASS, ASAS health index

- The average and raw (total and nocturnal) spinal pain NRS scores will be analyzed using a repeated measures analysis of variance (ANOVA) model with treatment, country and the stratification factor of prior exposure to TNF inhibitors (naïve/ inadequate responders to TNF α inhibitors) as factors and respective baseline NRS score as covariate. The least squares means of the two treatment groups, least squares mean difference and 95% confidence interval for the difference in the two treatment groups will be presented along with the p-value based on the fitted linear model.
- Formula for ASDAS-CRP calculation: ASDAS (CRP) = 0.121 x total back pain + 0,110 x patient global + 0.073 x peripheral pain/swelling + 0.058 x duration of morning stiffness + 0.579 x LN (CRP+1)
The parameters, which are taken from patient reported outcomes, are expected to have values 0-10. CRP needs to be in the unit mg/L.

All endpoints relating to exploratory objectives will be summarized descriptively. Summary statistics will include relative and absolute frequencies for the categorical variables and the number of patients (n), minimum, mean, median and maximum for continuous variables will be separately provided for both period I and period II. Time courses of response rates and mean NRS-scores will be displayed graphically.

The following categorical exploratory endpoints will also be summarized categorically as absolute and relative frequencies (proportions, %). Any improvement or reduction is referred to as 'response' for all the below mentioned endpoints.

- Proportion of patients in each treatment group with response in spinal pain score < 4 at Week 1, 2, 3 and 4.
- Proportion of patients in each treatment group with response in spinal pain score < 4 at Week 24.
- Proportion of patients in each treatment group with response in BASDAI score < 4 at Week 24.
- Proportion of patients in each treatment group with response in ASDAS score < 2.1 at Week 8 and Week 24.
- Proportion of patients in each treatment group with response in ASDAS score < 1.3 at Week 8 and Week 24.
- Proportion of patients in Arm 1 with spinal pain score > 6 at Week 12 or Week 24.
- Proportion of patients achieving a spinal pain score < 4 for TNF-naïve patients compared to TNF α -inadequate responder (TNF α -IR) patients at Week 8 and Week 24.
- Proportion of patients with response in spinal pain score < 4 to secukinumab 150 mg at Week 8 maintaining a response at Week 24. Only descriptive statistics will be presented for this endpoint.

The statistical significance of the above endpoints between groups will be analyzed by 95% CI of proportion. P-value will be added if there are enough number of patients available. The following continuous exploratory endpoints will also be summarized descriptively with number of patients (n), minimum, mean, standard deviation, median and maximum.

- Change from baseline in spinal pain score according to previous exposure to tumor necrosis factor (TNF) blockers at Week 1, 2, 3, 4, 8, 12 and 24.
- Change from baseline in total spinal pain score at all time points by each treatment group for each treatment period.
- Change from baseline in total BASDAI score at all time points by each treatment group for each treatment period.
- Change from baseline in ASDAS-CRP at Week 8 and Week 24.

If for a significant number of patients, the assignment to responder and / or non-responder status is incorrect, then a risk analysis may be performed.

